2. PROTOCOL SYNOPSIS

Title of Study	Bioequivalence study of Acyclovir 200 mg tablet manufactured by PT. Kimia Farma (Persero) Tbk in comparison with Zovirax® 200 mg tablet manufactured by Glaxo Wellcome S.A., Aranda, Spain, Packed by GlaxoSmithKline Australia Pty Ltd, Boronia Australia, imported by PT. Glaxo Wellcome Indonesia, Jakarta, Indonesia.
Objectives	The objective of this study is to investigate whether Acyclovir 200 mg tablet manufactured by PT. Kimia Farma (Persero) Tbk is bioequivalent to its reference product, Zovirax® 200 mg tablet manufactured by Glaxo Wellcome S.A., Aranda, Spain, Packed by GlaxoSmithKline Australia Pty Ltd, Boronia Australia, imported by PT. Glaxo Wellcome Indonesia, Jakarta, Indonesia.
Study Design	Randomized, single-blind, single-dose, 2-period, 2-treatment, 2-sequence, 2-way crossover study in healthy subjects under fasting condition.
Number of Subjects	28 healthy subjects
Washout period	1 week between each treatment
Test Product	
Name : Acyclovir 200 mg tablet
 
Manufacturer : PT. Kimia Farma (Persero) Tbk
 
Reg No : GKL9812415010A1
 
Batch No : C90576J
 
Mfg Date : March 2019
 
Exp Date : March 2024

Reference Product	
Name : Zovirax® 200 mg tablet
 
Manufacturer : Glaxo Wellcome S.A., Aranda, Spain, Packed by Glaxo-SmithKline Australia Pty Ltd, Boronia Australia, imported by PT. Glaxo Wellcome Indonesia, Jakarta, Indonesia.
 
Reg No : DKI1691601310A1
 
Batch No : 243E
 
Mfg Date : March 2018
 
Exp Date : March 2020

Inclusion Criteria	
 - have read the subject information and signed informed consent documents - healthy male and female - age 18 – 55 years - body mass index between 18–25 kg/m² - have a normal electrocardiogram - blood pressure within normal range (systolic 90-120 mmHg and diastolic 60-80 mmHg) - heart rate within normal range (60-100 bpm) - absence of significant disease or clinically significant abnormal laboratory values on laboratory evaluation, medical history or physical examination during screening

Exclusion Criteria	
 - pregnant and/or nursing women - history of contraindication or hypersensitivity to acyclovir, or other antiviral or other ingredients in the study products or a history of serious allergic reaction to any drug, a significant allergic disease, or allergic reaction - history or presence of medical condition which might significantly influence the pharmacokinetic of the study drug, e.g. chronic gastrointestinal disease, diarrhea, gastric surgery, renal insufficiency, hepatic dysfunction or cardiovascular disease. - history or presence of any coagulation disorder or clinically significant hematology abnormalities - using any medication (prescription or non-prescription drug, food supplement, herbal medicine), particularly the medication known to affect the pharmacokinetic of the study drug, within one week prior to the drug administration day - have participated in any clinical study within 3 months prior to the study (< 90 days) - have donated or lost 300 ml (or more) of blood within 3 months prior to the study - smoke more than 10 cigarettes a day - positive to HIV, HBsAg, and HCV tests (to be kept confidential) - history of drug or alcohol abuse within 12 months prior to screening for this study - unlikely to comply with the protocol, e.g uncooperative attitude, inability to return for follow up visits, poor venous access
Screening	
Medical history, physical examination, laboratory tests (routine hematology, blood biochemistry and urinalysis), electrocardiograph, pregnancy test and HIV, HBsAg, and HCV tests are carried out to screen the subjects and to obtain eligible subjects who meet the inclusion and exclusion criteria.

Subjects' Restriction	
 - Abstain from taking any medication at least one week before and during study period (unless necessary) - Not permitted to smoke, consume alcohol, milk, beverages or food containing xanthines (e.g., tea, coffee, chocolate) or fruit juice 24 hours prior and during study period - Instructed to avoid severe physical exertion during sampling hours
Standardization of study condition	
 - Subjects are instructed to stay one night before and during the sampling period - Subjects are instructed to fast from 8 hours before until 4 hours after drug administration - The menu served and meal taken by subjects are standardized and recorded - Water can be consumed as desired except during the period of 1 hour before until 2 hours after drug administration

Investigational Product Administration	A single dose of 200 mg acyclovir of the test drug or 200 mg acyclovir of the reference drug (according to randomization code) will be given orally to the subjects in sitting posture. The drug will be administered with 240 mL water.
Sampling Schedule	Blood samples for acyclovir assay (approximately 6 mL) are drawn into tubes containing anticoagulant (EDTA) before dosing (0 h) and at 15, 30, 45 min, 1, 1.5, 2, 2.5, 3, 4, 6, 8, 10, 12, 16 and 24 hours after dosing. The pre-dose sample (0 h) is collected within an hour before the first drug dosing SN01. A total volume of 192 mL of blood will be collected from each subject (2 periods x 16 sampling points x 6 mL per sampling point), 96 mL per period. This volume of blood will be used for pharmacokinetic analysis.
Subject Monitoring	Vital signs (blood pressure, pulse, respiration rate and body temperature) are monitored and recorded prior to drug administration, and subsequently at 1, 3, 6, 10, 12, and 24 hours after drug administration. The subjects' safety is monitored during the entire study under direct supervision by Study Physician at the study site.
Washout period	One week between each treatment
Analyte	Acyclovir concentration will be measured in plasma by a validated LC-MS/MS method. The LLoQ is 7.5 ng/mL for acyclovir.
Pharmacokinetics Parameter	C_{max} , AUC_t , AUC_{inf} , t_{max} and $t_{1/2}$ will be determined.
Statistical Analysis	Bioequivalence of the two formulations will be assessed by comparing the AUC_t and C_{max} of acyclovir values after ln transformation of the concentration data. The geometric mean ratios (test/reference) of the ln-transformed data and their 90% confidence intervals will be further analyzed with a parametric method (analysis of variance/ANOVA) using Equiv Test® version 2.0 (Statistical Solution Ltd., Saugus. MA, USA) or manual calculation which has been validated to Equiv Test®.
Bioequivalence Criteria	The two products are considered bioequivalent when the 90% confidence intervals of the acyclovir geometric mean ratio between test and reference products fall within the range of 80.00-125.00% for AUC_t and C_{max} .

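### Does the allowance for necessary medicines contradict the ban on medication in the week before dosing, and so leave it unclear who is dosed and analysed?

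*Combined protocol and SAP*

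**What the plan says.** All the relevant text is in section 2, Protocol Synopsis.

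- **Exclusion Criteria:** bars a subject "using any medication (prescription or non-prescription drug, food supplement, herbal medicine") if the use falls "within one week prior to the drug administration day". It states no exception, and the dosing day is in the singular.
- **Screening:** the assessments are made "to obtain eligible subjects who meet the inclusion and exclusion criteria", so entry to the study turns on those two lists.
- **Subjects' Restriction:** here the instruction to those enrolled reads "Abstain from taking any medication at least one week before and during study period (unless necessary"). It does not define necessity or say who judges it.
- **Washout period:** "One week between each treatment".
- **Study Design and Number of Subjects:** a two-period, two-sequence crossover in "28 healthy subjects".
- **Statistical Analysis and Bioequivalence Criteria:** ANOVA on ln-transformed AUC_t and Cmax, with 90% confidence intervals to lie within 80.00-125.00%. Neither row mentions medication use.

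**The concern.** Two rows of one table cover the week before dosing. One is absolute and the other carries an undefined exception. Someone who took a needed medicine in that week appears to be excluded by one row and compliant under the other.

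The washout sharpens the point. It equals the medication window, so anything taken between the periods falls both within the study period, where the exception is available, and within the week before the second dose. Staff could differ on whether such a subject goes on to Period 2.

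The statistical stake is the within-subject contrast. A medicine that alters acyclovir pharmacokinetics in one period only enters that subject's test/reference difference directly. If keeping or dropping the subject were settled after concentrations were known, a borderline interval could be moved across a limit.

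**Working it through.** The plan gives no figure to reproduce here: the synopsis states no CV, expected ratio, power or dropout rate. The check is a reading of the text, followed by a rough sizing.

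**1. Before Period 1.** Screening makes the inclusion and exclusion criteria the test of eligibility. The restriction list is not part of that test, and it does not say that its exception overrides a criterion. Read together, a subject may take a needed medicine without breaching an instruction and still meet an exclusion criterion. The bracketed exception also directly follows the reference to the study period and may qualify only that phrase. If so, no overlap remains before the first dose.

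**2. Before Period 2.** Washout of 7 days = medication window of 7 days, so the windows do coincide. A conflict needs a further premise: that the exclusion criterion is applied again before the second dose. The text does not say so, and its dosing day is singular. If it is not re-applied, the restriction alone governs the washout. If it is, the question arises only for a subject who takes a medicine in that week.

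**3. Analysis.** Neither medication row mentions the analysis, and the Statistical Analysis row does not mention medication. Silence is not contradiction.

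**4. Effect of one altered subject-period.** With 14 subjects per sequence (28/2, assuming balance), each subject's ln difference has weight 1/28. An f-fold change in k subjects, all in the same direction, multiplies the ratio by f^(k/28). The documents give no f, so a range is shown.

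| f (assumed) | k = 1 | k = 2 |
|---|---|---|
| 1.25 | 1.25^(1/28) = 1.008 | 1.25^(2/28) = 1.016 |
| 1.5 | 1.5^(1/28) = 1.015 | 1.5^(2/28) = 1.029 |
| 2 | 2^(1/28) = 1.025 | 2^(2/28) = 1.051 |

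Against the distance from a ratio of 1 to a limit, ln 1.25 = 0.2231, one subject at f = 1.5 uses ln(1.5)/28 = 0.0145, or 0.0145/0.2231 = 6.5%. Sequence is randomised, so a washout medicine could fall before either product. It has no built-in direction unless the Period 1 product caused the need for it.

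**5. Effect of losing subjects.** Power of two one-sided tests, each at 5%, for a 2x2 crossover:

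- s = √ln(1 + CV²); standard error = s·√[½(1/n₁ + 1/n₂)]; n − 2 degrees of freedom.
- Limits ±ln 1.25; result integrated over the chi-square distribution of the variance estimate.
- Assumed true ratio 0.95. CV is also assumed.

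| CV | n = 28 | n = 26 | n = 24 | Loss of 2 (points) | Loss of 4 (points) |
|---|---|---|---|---|---|
| 20% | 93.5% | 91.8% | 89.6% | 1.7 | 3.9 |
| 25% | 80.7% | 77.6% | 73.9% | 3.1 | 6.8 |
| 30% | 64.8% | 60.6% | 55.8% | 4.2 | 9.0 |
| 35% | 48.1% | 43.2% | 37.8% | 4.9 | 10.3 |

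These losses are the price of dropping subjects under any rule. They do not measure harm done by the wording.

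**The case for a change.** The strongest opposing case is that the reader should not have to choose between readings. The split between eligibility and conduct is inferred, the bracket's reach is not settled by the syntax, and the restriction plainly extends back into the week that the exclusion covers. Even if the bracket qualifies only the study period, the washout stays open, because it is both study period and pre-dose week. The exclusion row itself gives effects on pharmacokinetics as a particular reason for the ban, and the pass/fail limits are fixed. Clarifying wording is cheap, as is a decision recorded before concentrations are available.

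Part of this stands. The wording is uneven, and the scope by period is unstated. If the synopsis is reissued for other reasons, the sponsor can reconcile the two rows; which clinical rule should govern is not a matter for this review.

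The larger claims do not stand. The issue does not recur for every subject: it needs someone screened for recent medication and told to abstain to take a medicine in a particular week. Nothing in the text provides for a decision after the concentrations are known; that possibility is inferred from one synopsis row saying nothing. The text available is a synopsis, so a missing deviation or analysis-set rule there is weak evidence that none exists.

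**Conclusion.** The concern identifies a real ambiguity, but not an error that calls for a change. Followed as written, the plan screens out those who used medication before dosing and tells enrolled subjects to abstain, with room for necessary medicines. That supports a sound comparison. Rewording would record a clarification and a data-handling policy, but it would not correct a number, an estimate or the bioequivalence rule. Competent analysts would record any medication use as a deviation and settle its handling before seeing concentrations, without needing the synopsis to say so.

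The likely size is small. One affected subject of 28 moves the ratio by about 0.8% to 2.5% for assumed 1.25- to 2-fold changes. Dropping two costs about 2 to 5 points of power for assumed CVs of 20% to 35% at a true ratio of 0.95. Fold change, CV, true ratio and number affected are all assumptions. The conclusion rests mainly on the reading of the rows. It would weaken if another part of the protocol re-applied the exclusion before Period 2 and still allowed the exception.

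### The synopsis applies the ln transformation to the concentrations, but the AUC_t criterion needs ln of each subject's AUC_t (minor, probably a drafting error)

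*Combined protocol and SAP*

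**What the plan says.** All references are to the combined protocol and SAP, section 2 (Protocol Synopsis).

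- **Statistical Analysis row, first sentence.** The two formulations are compared on AUC_t and Cmax "of acyclovir values after ln transformation of the concentration data".
- **Statistical Analysis row, next sentence.** "The geometric mean ratios (test/reference) of the ln-transformed data and their 90% confidence intervals" go into a parametric ANOVA, run either in a named software package or by a manual calculation validated against it.
- **Bioequivalence Criteria row.** The products are bioequivalent when "the 90% confidence intervals of the acyclovir geometric mean ratio between test and reference products fall within the range of 80.00-125.00" percent, for both AUC_t and Cmax.

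The first sentence is the only one in the available text that says what is ln-transformed. The second refers back to it and does not name the variable again.

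**The concern.** A geometric mean ratio of AUC_t is obtained by taking ln of each subject's AUC_t, estimating the test-minus-reference difference on that scale, and exponentiating. The first sentence puts the ln step earlier, on the concentrations from which AUC_t is calculated. Integration and the logarithm do not commute, so that order does not produce the quantity the criterion tests.

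AUC_t is one of the two variables that decide bioequivalence, so the sentence is the stated rule for a primary analysis. The plan also allows manual calculation, where someone works from the written steps, so those steps should be right.

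**Working it through.** The plan gives no figure that depends on this step, so there is none to reproduce. The check is what each reading of the ln step gives.

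**Inputs from the synopsis.** Limits 80.00-125.00%; "28 healthy subjects"; "2 periods x 16 sampling points x 6 mL per sampling point"; samples "before dosing (0 h) and at 15, 30, 45 min" and onward to 24 h; "The LLoQ is 7.5 ng/mL for acyclovir".

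**1. Scale of the criterion.** ln(0.80) = -0.223 and ln(1.25) = +0.223. The limits are symmetric for a difference in ln(parameter), which is the scale a geometric mean ratio uses.

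**2. Cmax.** ln is increasing, so max(ln C) = ln(max C) = ln(Cmax). Both readings give the same ratio.

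**3. AUC_t, dependence on the unit.** Take flat profiles over the same time span, with test at 0.80 times reference. The span cancels, so the ratio of ln areas is ln(C_test)/ln(C_ref). At the LLoQ, 7.5/0.80 = 9.375 ng/mL for reference:

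- ng/mL: ln 7.5 / ln 9.375 = 2.015/2.238 = 0.900
- ug/mL: ln 0.0075 / ln 0.009375 = (-4.893)/(-4.670) = 1.048

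Other levels, which are assumed and not in the documents:

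| Test / reference (ng/mL) | True ratio | ln-area ratio, ng/mL | ln-area ratio, ug/mL | Difference in ln(AUC_t), either unit |
|---|---|---|---|---|
| 7.5 / 9.375 | 0.80 | 0.900 | 1.048 | -0.223 |
| 80 / 100 | 0.80 | 0.952 | 1.097 | -0.223 |
| 320 / 400 | 0.80 | 0.963 | 1.244 | -0.223 |

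**4. AUC_t, an oral-shaped profile.** This uses the plan's 16 sampling times and LLoQ with an assumed one-compartment curve (absorption rate 1.0/h, elimination rate 0.25/h, peak 300 or 600 ng/mL). Test is a constant multiple of reference, and areas are linear trapezoids over samples at or above the LLoQ.

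| True AUC_t ratio | ln-area ratio, peak 300 | ln-area ratio, peak 600 | Ratio from ln of AUC_t |
|---|---|---|---|
| 0.70 | 0.918 | 0.929 | 0.70 |
| 1.00 | 1.000 | 1.000 | 1.00 |
| 1.40 | 1.078 | 1.067 | 1.40 |

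Exponentiating the difference of the ln areas does not help. With test = R x reference, that difference is (time span) x ln R. The usable samples run from 0.25 to 16 h, a span of 15.75 h, so the result is R^15.75: 0.70^15.75 = 0.0036 and 1.40^15.75 = about 200. Neither is a bioavailability ratio.

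**5. Zero concentrations.** ln(0) is undefined. Scheduled samples: 28 x 2 x 16 = 896. Pre-dose samples: 28 x 2 = 56, and 56/896 = 6.25%. Each would fail under the literal rule if it is drug-free and recorded as zero.

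**The case against.** The best reply is that nobody would carry out the literal rule. The sentence itself names AUC_t and Cmax, the next one speaks of geometric mean ratios and ANOVA, and the criterion applies to the geometric mean ratio. On that reading, the reference to concentration data is loose wording for the parameters derived from concentrations. The plan also never defines AUC_t as an area under ln concentration. The estimators in the check had to be supplied, they disagree with each other, and the profiles are artificial.

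Much of this stands. The intent is clear, Cmax is unaffected, and the numbers show only that the literal quantity is not the geometric mean ratio. They say nothing about this trial's result. A shorter rewording would also remove the error.

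It does not make the sentence right. The available text nowhere says that ln is applied to the individual parameters. The following sentence refers to the ln-transformed data, which leads back to the faulty phrase. That the literal wording yields no usable AUC_t estimator is itself the reason to correct it.

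**Conclusion.** The concern holds, as a minor point. The wording is wrong for AUC_t and harmless for Cmax. Followed literally, it gives a quantity that is unit-dependent, undefined at zero, and not comparable with 80.00-125.00%. The context points to a drafting error, so no direction of bias and no effect on the probability of concluding bioequivalence is claimed.

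Confidence is high for the wording only. The unit example takes the LLoQ and the 80% limit from the plan and assumes flat profiles. The oral-shaped example rests on assumed kinetics. Only the synopsis was available, so a fuller statistical section, if there is one, could not be checked. If it states the step correctly, the synopsis still needs to be aligned with it.

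**What to change.** Replace the first sentence of the Statistical Analysis row with:

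> AUC_t and Cmax are calculated from the untransformed plasma concentrations. The individual AUC_t and Cmax values are then ln-transformed and analysed by the crossover ANOVA. The test/reference geometric mean ratio and its 90% confidence interval are obtained by exponentiating the formulation difference and its confidence limits.

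The minimum change is to make the individual AUC_t and Cmax values, rather than the concentrations, the object of the ln transformation. Any fuller statistical section should use the same wording. The cost is one to three sentences, with no new data, samples or subjects.
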